3.3 Data Collection and Statistical Considerations

Data collection is summarized in Table 1. Body temperature and pulse oximetry will be checked by the inpatient nursing staff at least three times daily, beginning with randomization and ending with resolution of fever and hypoxemia, respectively, or study completion. Body temperature and pulse oximetry orders will be entered into the electronic medical record by a member of the research staff if not already ordered as part of standard of care. Documentation will be entered into the electronic medical record in the form of a research progress note informing the treating physician of vital signs ordered for research purposes to avoid duplication of tasks. The visual analog scale (VAS) for pain will be assessed once daily beginning with randomization and ending with resolution of moderate to severe pain or study completion. Laboratory evaluation will include a complete blood count (white blood cell count, hemoglobin and hematocrit, and platelet count). Complete blood count (white blood cell count) will be obtained daily beginning with randomization and ending with resolution of leukocytosis or study completion. Complete blood count (hemoglobin, hematocrit, and platelet count) will be obtained daily beginning with randomization and ending with study completion in subjects receiving UFH. Anti-Xa UFH level will be ordered according to the heparin infusion protocol as detailed earlier in subjects receiving UFH. Complete blood count will be entered into the electronic medical record by a member of the research staff if not already ordered as part of standard of care. Documentation will be entered into the electronic medical record in the form of a research progress note informing the treating physician of laboratory studies ordered for research purposes to avoid repeat blood draws. All blood samples will be collected by the inpatient phlebotomy team or nursing staff and sent to the inpatient laboratory for analysis.

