Further data collected will include information regarding standard of care therapy (collected daily during duration of study), demographics (collected following study enrollment and screening), and medical information (collected following study enrollment and screening). Regarding standard of care therapy, data collected will consist of whether or not intravenous fluids were given; whether or not antibiotics were administered, number of antibiotics received, and class of antibiotics given (penicillin, cephalosporin, macrolide, fluoroquinolone, vancomycin, other); whether or not supplemental oxygen was received with documentation of need for noninvasive positive pressure ventilation or mechanical ventilation; whether or not pain medication was provided, including type of pain medication (opioid, NSAIDs, acetaminophen, other); number of red blood cell transfusions given; and whether or not exchange transfusion was necessary. Demographics include age, race, and sex. SCD related medical information includes number of previous episodes of ACS, current administration of outpatient hydroxyurea, and prior DVT or PE. General medical information includes history of myocardial infarction; chronic lung disease, defined as a documented baseline arterial oxygen saturation less than 90% and/or home supplemental oxygen requirement; previous stroke; and current or former smoker.

Prespecified feasibility criteria are as follows: the ability to enroll potential study participants, which includes the timely notification of hospitalized patients with ACS, the capacity to consent eligible individuals, and the ability to appropriately randomize screened patients within 24 hours of diagnosis, all of which should occur at a frequency greater than or equal to 80%; inclusion and exclusion criteria that does not exclude potential study participants at a frequency greater than or equal to 20%; the proper administration of the study drug at a frequency greater than or equal to 90%; and the ability to completely and accurately collect clinical data of interest at frequency greater than or equal to 90%. The final aim of our pilot study is to provide preliminary data, with respect to treatment effect and variance, for future sample size calculations given the lack of existing data to help guide this process.

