the patient has a baseline supplemental oxygen requirement, hypoxemia will be defined as an increase in supplemental oxygen requirement above the patient's baseline. If the patient does not meet criteria for hypoxemia following the initial 3 nursing vital signs assessments after randomization, hypoxemia will be considered absent and no further assessments will occur. Resolution of hypoxemia will be defined as failure to meet the criteria for hypoxemia on 3 consecutive nursing vital signs assessments. Duration of fever will be defined as beginning with randomization and measured in hours. Fever will be defined as a body temperature greater than or equal to 38.0 degrees Celsius measured by a thermometer orally. If the patient does not meet criteria for fever following the initial 3 nursing vital signs assessments after randomization, fever will be considered absent and no further assessments will occur. Resolution of fever will be defined as failure to meet the criteria for fever on 3 consecutive nursing vital signs assessments. Duration of leukocytosis will be defined as beginning with randomization and measured in hours. Leukocytosis will be defined as a white blood cell count greater than 10,000 per liter. If the patient does not meet criteria for leukocytosis following the initial 2 complete blood counts after randomization, leukocytosis will be considered absent and no further assessments will occur. Resolution of leukocytosis will be defined as failure to meet the criteria for leukocytosis on 2 consecutive complete blood counts. Duration of moderate to severe pain will be defined as beginning with randomization and measured in hours. If the patient does not report a score of 4 or greater on the VAS for pain following the initial 2 assessments after randomization, moderate to severe pain will be considered absent and no further assessments will occur. The end of the duration of moderate to severe pain will be defined as 2 consecutive scores of less than 4 on the VAS for pain. Total dose of opioids will be defined as beginning with randomization, ending with study completion, and measured in milligrams of oral morphine equivalents. Red blood cell transfusions will be given routinely as standard clinical practice in acute chest syndrome with the goal of preventing progression to acute respiratory failure. Number of red blood cells transfused will be defined as beginning with randomization, ending with study completion, and measured in units of packed red blood cells received. Red blood cell transfusions given for suspected or proven hemorrhage secondary to UFH will not be included in the outcome as defined above. Rate of transfer to the ICU, requirement for mechanical ventilation, and development of MODS will be defined as beginning with randomization, ending with study completion, and categorized as present or absent. Further, MODS will be defined as the acute development of 2 or more organs or organ systems unable to maintain homeostasis in a critically ill individual.

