4.3 Inclusion/Exclusion Criteria

Inclusion criteria:

1. Diagnosis of ACS defined as a new pulmonary infiltrate involving at least one segment of the lung on a chest x-ray or chest CT scan with 2 or more of the following: chest pain, tachypnea (defined as a respiratory rate greater than 20 breaths per minute), dyspnea, cough, hypoxemia (see 3.3 Data Collection and Statistical Considerations for definition of hypoxemia), or body temperature greater than or equal to 38.0 degrees Celsius.

2. Hemoglobin electrophoresis confirming (HbSS, SC, or S β^0) (historical records sufficient).

3. Age greater than or equal to 18.

Exclusion Criteria:

1. Any absolute contraindication to heparin, including known bleeding diathesis, history of HIT, or history of an allergic reaction.

2. Platelet count less than 50 per microliter (current admission).

3. Historical diagnosis of moyamoya disease as documented in medical records.

4. Historical diagnosis of proliferative retinopathy as documented in medical records.

5. Current participation in a chronic exchange transfusion program.

6. Underlying hypercoagulable disorder other than SCD.

7. Currently receiving therapeutic anticoagulation.

8. Currently receiving antiplatelet agents.

9. Currently receiving estrogen containing oral contraceptives.

10. Chest CT scan documented PE performed as standard of care prior to study enrollment (current admission).

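### Symptoms that begin after the first checks are recorded as absent, and open episodes, withdrawals and deaths have no stated duration, so the effect and variance passed to phase III depend on unstated coding choices

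*Combined protocol and SAP*

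**What the plan says.** Section 3.3 defines four symptom or laboratory durations, each counted in hours from randomization, with the same rules in both arms.

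- **Schedule.** Temperature and oximetry are "checked by the inpatient nursing staff at least three times daily", "ending with resolution of fever and hypoxemia, respectively, or study completion". Blood counts and the pain VAS are daily.
- **Absence.** After three checks without hypoxemia, "hypoxemia will be considered absent and no further assessments will occur". Fever is treated alike. After two clear blood counts, "leukocytosis will be considered absent and no further assessments will occur", and two low VAS scores do the same for pain.
- **Resolution.** "Resolution of hypoxemia will be defined as failure to meet the criteria for hypoxemia on 3 consecutive nursing vital signs assessments". Fever also needs three; leukocytosis and pain need two.
- **Other daily data.** Section 3.3 also records each day "whether or not supplemental oxygen was received with documentation of need for noninvasive positive pressure ventilation or mechanical ventilation".
- **Entry.** Section 4.3 asks for a new infiltrate "with 2 or more of the following: chest pain, tachypnea", dyspnea, cough, hypoxemia or raised temperature. Neither hypoxemia nor fever is required.
- **Endings.** Hospitalization, the primary clinical outcome, ends at the discharge order (section 3.3). Section 4.2 keeps data gathered before a withdrawal and collects none after it. Study completion is not defined; heparin runs for seven days or to earlier discharge (section 3.2), and Table 1 stops at Day 7.
- **Analysis.** For continuous variables section 3.3 names mean, median, range and standard deviation. Its final aim is an effect and a variance from which to size a later trial.

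**The concern.** There are two separate problems.

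The first is a rule that misclassifies. A patient who is clear early and later becomes hypoxemic or febrile is recorded as never having had the condition, and a return after resolution is not counted. Section 2.2 itself describes the course as hard to predict. The same patient could be listed as newly on oxygen and as never hypoxemic. Table 1, which shows assessments on all seven days, does not mention the early stop.

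The second is a missing rule. Three kinds of patient have no completed duration: those with an episode still open at study completion, those who withdraw, and those who die before a discharge order. The plan does not say whether they are entered at their last time, entered at some cut-off, or left out. Because the trial is open-label, that choice would be made by people who have seen the data and know the arms. Effect and variance, the two quantities the pilot is meant to hand on, both depend on it.

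**Working it through.** The plan gives no figure for this point. The sample size of 20 is stated to rest on clinical grounds. Only its accrual arithmetic can be checked, and it agrees: 30 × 0.80 = 24 eligible a year, and 10/24 = 42% enrolled. The sizes below therefore use assumed inputs.

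**1. When absence is fixed.** At three checks a day, the first and third are 2 × 8 = 16 h apart. Once absence is declared, up to 168 − 16 = 152 h of a seven-day period have no outcome assessment.

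**2. How many patients.** Assume 30% to 50% are clear on the first three checks and 10% to 30% of those become hypoxemic later. Expected misclassified: 20 × 0.3 × 0.1 = 0.6 to 20 × 0.5 × 0.3 = 3.0. Chance of at least one: 1 − 0.9^6 = 47% to 1 − 0.7^10 = 97%.

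**3. Effect on the arm mean.** Assume lognormal durations with log-SD 0.7, median 48 h for early episodes and 36 h for late ones. The means are 48·exp(0.245) = 61.33 h and 36·exp(0.245) = 45.99 h.

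| Scenario | All episodes, absent = 0 h | Under the rule, absent = 0 h | All episodes, absent left out | Under the rule, absent left out |
|---|---|---|---|---|
| 30% clear, 10% of them late | 0.70 × 61.33 + 0.03 × 45.99 = 44.3 | 42.9 (3% low) | 44.31/0.73 = 60.7 | 61.3 (1% high) |
| 50% clear, 30% of them late | 0.50 × 61.33 + 0.15 × 45.99 = 37.6 | 30.7 (18% low) | 37.56/0.65 = 57.8 | 61.3 (6% high) |

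The sign depends on the coding of absent, which the plan does not give.

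**4. Effect on phase III size.** Take n per arm = 7.85 × (SD_A² + SD_B²)/d² (two-sided 5%, 80% power), early episodes 20% shorter on heparin, absent = 0 h. If heparin does not alter late onset, n changes by −5% to +1%. If heparin also halves late onset (a further assumption), the rule moves n from 366 to 429 in the mildest scenario and from 309 to 729 in the worst. The difference then shifts by 45.99 × 0.03 × 0.5 = 0.7 h to 45.99 × 0.15 × 0.5 = 3.4 h, against a pilot standard error of 19 to 20 h.

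**5. Open episodes.** Assume a cut-off at 168 h, lognormal durations and heparin 20% shorter. With M = median·exp(σ²/2) and a = ln(168/median)/σ, the mean is M·Φ(a − σ) + 168·(1 − Φ(a)) if open episodes are entered at 168 h, and M·Φ(a − σ)/Φ(a) if they are left out. For control median 96 h and σ = 0.8: M = 132.2, Φ(a − σ) = 0.460 and 1 − Φ(a) = 0.242, giving 60.8 + 40.7 = 101.5 h entered and 60.8/0.758 = 80.2 h left out. The heparin arm (median 76.8 h) gives 87.9 and 72.2 h.

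| Control median, log-SD | Open, of 20 | Entered at 168 h | Left out |
|---|---|---|---|
| 48 h, 0.6 | 0.25 | difference 10.9 h, n = 130 | difference 9.7 h, n = 139 |
| 96 h, 0.8 | 4.1 | difference 13.6 h, n = 221 | difference 8.0 h, n = 386 |

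For the second row, entered: 7.85 × (51.3² + 50.6²)/13.58² = 221. Left out: 7.85 × (40.1² + 39.5²)/8.03² = 386. The two codings differ by 139/130 = 1.07 times in the mild case and 386/221 = 1.7 times in the other.

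**6. Sampling error for scale.** In the second row, the standard error of the entered difference with 10 per arm is √((51.3² + 50.6²)/10) = 22.8 h, and the codings differ by 13.6 − 8.0 = 5.6 h. The 95% interval for a variance on 18 df is 18/χ² = 0.57 to 2.19 times the estimate.

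**7. Deaths and the primary outcome.** Section 2.1 cites 9% mortality in adults. If that applied here, P(at least one death in 20) = 1 − 0.91^20 = 85%; at an assumed 3% to 5% it is 46% to 64%. One death at 48 h in an arm whose other nine stays average 144 h (assumed) gives a mean of (9 × 144 + 48)/10 = 134.4 h if time to death counts as the stay, 144 h if left out, and (9 × 144 + 168)/10 = 146.4 h if set to 168 h. The first choice makes the arm with the death look better.

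**The case against.** The best defence is that time to first resolution of the presenting episode is a legitimate outcome, prespecified and identical in both arms. Later severe worsening is captured by ICU transfer, mechanical ventilation and multiorgan dysfunction, and oxygen use is recorded daily. Comparisons are descriptive with 10 per arm. Nothing says that phase III will be sized on a symptom duration, and hospitalization has a clear start and end. All of this stands, and it limits the weight of the point. It does not make late hypoxemia absent, and it does not supply the missing rules.

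Three stronger readings are tempting, and the document does not support them.

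- *The absence rule pulls the means down.* That needs absent to be coded as 0 h, which is not stated. If absent patients are left out, the sign reverses (step 3).
- *Entering open episodes at 168 h distorts the effect.* With complete follow-up, that average is the restricted mean to 168 h, a sound estimand. In the 96 h scenario the unrestricted difference is 26.4 h, but a seven-day schedule cannot observe it. The fault is that no choice is stated.
- *The rule favours heparin.* It is the same in both arms and hardly changes phase III n unless heparin alters late onset, on which the document has no data. One asymmetry is real: blood counts continue to study completion only in patients on heparin, so late leukocytosis could be seen in one arm only.

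**Conclusion.** The point holds as a misclassifying definition plus a missing rule, and should be corrected. Late episodes of four secondary outcomes are recorded as absent, and incomplete durations have no assigned value while effect and variance are wanted for phase III. The list of summaries in section 3.3 is introduced as non-exhaustive, but no method that handles incomplete durations is named.

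The size is modest. Late onset shifts an arm mean by 3% to 18% downward or 1% to 6% upward, according to coding. The choice for open episodes moves phase III n per arm between 130 and 139 in the mild case and between 221 and 386 in the heavier one. These figures rest on the lognormal shapes, medians, 20% effect, late-onset rates and 168 h cut-off assumed above; none is in the document. All are small beside the sampling error of 10 per arm. The primary outcome is touched only through deaths, withdrawals and, if Day 7 is read as the cut-off, longer stays.

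**What to change.** 1. **Symptom durations.** Label each one *episode present at randomization*. Report by arm how many patients had none, and summarise duration among those who had one. Alternatively, use a restricted mean with absent as 0 h. Avoid a median that includes the zeros: with log-SD 0.7 and 30% clear, the arm medians fall from 48 and 38.4 h to 32.3 and 25.8 h, and with 50% clear both are 0 h and the effect disappears. For hypoxemia and fever, replace the absence wording with a count by arm of patients with onset or recurrence after the initial checks, taken from the daily oxygen record and routine vital signs. Label leukocytosis and pain *initial episode only*, and do not use the extra Arm A blood counts for them. Reconcile Table 1 with this.
2. **Incomplete durations.** Define study completion, including whether discharge ends it. Censor open episodes there and withdrawals at withdrawal. Count a patient who dies before resolution as unresolved to the cut-off. Report the restricted mean time to a stated cut-off with its standard error, and the number unresolved by arm.
3. **Hospitalization.** Take the discharge-order time even after Day 7. Analyse time to discharge alive, with deaths kept as never discharged and withdrawals censored, and list deaths by arm.
4. **Phase III sizing.** Take effect and variability from the same definition.

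The cost is a few sentences and slightly more programming, with no added patients or tests. Oxygen use is already recorded daily. Counting late fever assumes that routine vital signs continue after the research requirement ends.

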3.2 Study Design

This is a single-center, randomized controlled, open-label, pilot study to determine the feasibility of performing a larger multicenter phase III trial to assess the effects of UFH in ACS. Adult patients with SCD (HbSS, SC, or Sβ⁰) aged 18 years or older admitted to UPMC (Presbyterian, Montefiore, Magee, Shadyside) hospitals with a diagnosis of ACS will be eligible for screening to participate in the trial. Subjects meeting inclusion and exclusion criteria and consenting to study will be randomized within 24 hours of diagnosis to one of two treatment arms, Arm A, anticoagulation and standard of care, or Arm B, no anticoagulation and standard of care. Weight-adjusted UFH will be given at doses of 80 units per kilogram followed by 18 units per kilogram per hour intravenously for 7 days, or until discharge, if discharge is shorter than 7 days. UFH will be monitored by standard protocol to maintain the anti-Xa UFH level in the therapeutic range per institutional guidelines.¹⁵ During the study period, if therapeutic anticoagulation is indicated for non-research purposes, it will be given at the discretion of the treating physician.

Standard of care, per the treating physician, will include the following:

- Intravenous fluids, preferably hypotonic saline, will be given to maintain adequate hydration. The specific rate, subsequent changes in rate, and duration will be per the treating physician's discretion.
- Antibiotics will be given to treat pathogens that are responsible for community acquired pneumonia, such as "atypicals" or, if necessary, to provide a broader spectrum of coverage against antimicrobial organisms as the treating physician sees fit.
- Supplemental oxygen will be provided to maintain the arterial oxygen saturation, as recorded by pulse oximetry, greater than or equal to 90%.
- Incentive spirometry will be provided with recommendations to take 10 breaths every 2 hours while awake.
- Pain management will consist of acetaminophen, nonsteroidal antiinflammatory drugs (NSAIDs), or opioids as needed to maintain adequate analgesia. Specifics regarding pain management will be individualized according to each patient's established plan of care as dictated by his or her outpatient hematologist.
- Red blood cell transfusions will be given routinely as standard clinical practice in acute chest syndrome with the goal of preventing progression to acute respiratory failure.

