The primary clinical outcome is duration of hospitalization. Secondary clinical outcomes include the duration of hypoxemia, duration of fever, duration of leukocytosis, duration of moderate to severe pain, total dose of opioids, and the number of red blood cell transfusions administered. Additional clinical outcomes will include the rate of transfer to the ICU, requirement for mechanical ventilation, and development of MODS.

Duration of hospitalization will be defined as beginning with randomization and measured in hours. Conclusion of hospitalization will be defined as the time of order entry into the inpatient electronic medical record system stating the patient is appropriate for medical discharge, per the discretion of the treating physician. Duration of hypoxemia will be defined as beginning with randomization and measured in hours. Hypoxemia will be defined as arterial oxygen saturation less than 90% according to pulse oximetry and/or the continued need for supplemental oxygen. If the patient's baseline arterial oxygen saturation is less than 90%, hypoxemia will be defined as a decrease in arterial oxygen saturation below the patient's baseline. Similarly, if

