Heparin therapy, like any other form of anticoagulation, increases the risk of bleeding. The risk of bleeding with UFH varies among clinical settings. The risk of bleeding with intravenous UFH in acute VTE is less than 3%.²⁰ Bleeding may be major, defined as a decrease in hemoglobin 2 grams per deciliter or more; transfusion of 2 or more units of red blood cells; or bleeding in a critical organ, such as intracranial, intraspinal, intraocular, pericardial, or retroperitoneal.²¹ The presence of major bleeding will result in the permanent discontinuation of UFH. If major bleeding occurs, protamine will be administered to reverse the anticoagulant effects of heparin. Protamine may result in hypotension, bradycardia, dyspnea, flushing, feeling of warmth, nausea, vomiting, or rarely anaphylaxis.¹⁴ Other medical interventions, such as intravenous fluids and red blood cell transfusions, will be administered as deemed appropriate. Minor bleeding is defined as all bleeding episodes that do not meet criteria for major bleeding. The treatment of minor bleeding may vary and will be determined by the specific clinical scenario. The decision to discontinue UFH in the setting of minor bleeding, permanently or only for a brief period of time, will be at the investigator's discretion. A known history of a bleeding diathesis will result in exclusion from study participation.

3. Thrombocytopenia

The risk of non-immune related thrombocytopenia with heparin varies anywhere between 5 and 30%.²² Thrombocytopenia will be defined as a platelet count less than 100,000 per microliter. UFH will be discontinued if the platelet count is less than 50,000 per microliter and may be resumed if the platelet count increases to greater than 50,000 per microliter during the study period. A baseline platelet count less than 50,000 per microliter will result in exclusion from study participation.

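### Leukocytosis is defined per liter instead of per microliter, so as written it is always present, never resolves, and its duration only measures observation time

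*Combined protocol and SAP*

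**What the plan says.** Duration of leukocytosis is one of the secondary clinical outcomes in Section 3.3: "Secondary clinical outcomes include the duration of hypoxemia, duration of fever, duration of leukocytosis, duration of moderate to severe pain". The same section gives the threshold: "Leukocytosis will be defined as a white blood cell count greater than 10,000 per liter". This is the only numerical definition of leukocytosis in the document.

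Four rules in Section 3.3 depend on it:

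- Start and unit: "Duration of leukocytosis will be defined as beginning with randomization and measured in hours".
- Absence: "If the patient does not meet criteria for leukocytosis following the initial 2 complete blood counts after randomization, leukocytosis will be considered absent".
- Resolution: "Resolution of leukocytosis will be defined as failure to meet the criteria for leukocytosis on 2 consecutive complete blood counts".
- Sampling: "Complete blood count (white blood cell count) will be obtained daily beginning with randomization and ending with resolution of leukocytosis or study completion".

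Elsewhere, blood-count limits are given per microliter. Section 4.4, for example, has "Thrombocytopenia will be defined as a platelet count less than 100,000 per microliter".

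**The concern.** A limit of 10,000 per liter is far below any white count a laboratory would report. If no patient can be at or below it, the absence and resolution rules have nothing to act on and the outcome stops describing leukocytosis.

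Section 3.3 says a final aim of the pilot is to estimate treatment effect and variance so that a later trial can be sized. Under the written limit, this outcome's mean, standard deviation and difference between arms would describe how long patients were observed. The rule that ends daily white counts at resolution would also never take effect.

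**Working it through.** **Inputs**

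| Input | Value | Source |
|---|---|---|
| Threshold as written | above 10,000 per liter | Section 3.3 |
| Absent | criterion not met on the first 2 counts | Section 3.3 |
| Resolved | criterion not met on 2 consecutive counts | Section 3.3 |
| Sampling | daily, to resolution or study completion | Section 3.3 |
| Observation period | up to 7 days (7 × 24 = 168 h), or discharge if earlier | inferred from the infusion period in Section 3.2 and from Table 1 |
| Planned patients | 20 | Section 3.3 |
| White counts | assumed 100 to 30,000 per microliter | assumption; the document gives none |

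The threshold is a definition and not a calculated figure, so there is no figure of the plan's own to reproduce.

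**Step 1: convert the unit.** 10,000 per liter ÷ 1,000,000 microliters per liter = 0.01 per microliter. In the other direction, 10,000 per microliter × 1,000,000 = 10^10 per liter. The ratio is 10^10 ÷ 10^4 = 10^6.

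**Step 2: compare with possible counts.**

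- 1 per microliter = 1,000,000 per liter, and 1,000,000 ÷ 10,000 = 100 times the written limit.
- 100 per microliter = 10^8 per liter, which is 10,000 times the limit.
- 30,000 per microliter = 3 × 10^10 per liter, which is 3,000,000 times the limit.

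Every value in the assumed range is positive, by at least four orders of magnitude, so the result does not depend on where in the range patients fall.

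**Step 3: apply the plan's own rules.** The series below are illustrative daily counts per microliter, the first at 0 h.

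| Illustrative patient | As written (per liter) | Read per microliter |
|---|---|---|
| 9,000 falling to 8,000, observed 168 h | 168 h | absent |
| 18,000 at 0 h, 9,800 at 72 h, 9,500 at 96 h, observed 168 h | 168 h | resolved at 72 to 96 h |
| 15,000, 9,900, 9,000, 8,500, discharged at 96 h | 96 h | resolved at 24 to 48 h |
| 22,000 falling to 13,000, observed 168 h | 168 h | 168 h |

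As written, each duration equals the observation time. The ranges in the last column arise because Section 3.3 does not say whether the first or the second negative count ends the duration. With daily draws that leaves about 24 hours open.

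**Step 4: look for a correction elsewhere.** None was found. A symbol lost in text extraction is unlikely, because liter is spelled out here and microliter is spelled out for platelets in Sections 4.3 and 4.4.

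**The case against.** The strongest reply is that this is an obvious slip. The paragraph that sets the limit also says when leukocytosis is absent or resolved, which makes sense only if the limit can be crossed. Staff reading ordinary laboratory reports would probably apply 10,000 per microliter without noticing. The finding of 20 positive patients out of 20 is therefore what a literal reading yields, not a forecast of what the trial will record.

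The data would also be recoverable. Under literal use the daily counts continue and stay in the electronic record, so durations could be re-derived. If staff use the intended limit, the outcome is already right.

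The extra blood draws are limited too. Section 3.3 requires daily hemoglobin, hematocrit and platelet counts to study completion in patients receiving heparin. The lost stopping rule therefore matters mainly in the standard-of-care arm (10 patients), and only where a count was not already ordered clinically.

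Finally, this is one of six secondary outcomes in Section 3.3, summarized descriptively. No test, sample size or feasibility threshold depends on it.

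All of this stands, and it limits the practical harm. It does not rescue the definition, because each point assumes that someone departs from the text. A prespecified outcome should not rely on silent correction. Re-deriving it after the data have been seen, in an open-label trial, is weaker than having it right beforehand.

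**Conclusion.** The concern holds for the outcome as defined. The written limit is too low by a factor of 1,000,000, on the reading that per microliter was intended. Under it, all 20 planned patients would be positive at every draw, none could be absent or resolved, and duration would equal time from randomization to study completion.

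The conclusion rests on two assumptions. First, white counts lie anywhere near the assumed range; the margin is so wide that this is hardly a restriction. Second, study completion, which the document does not expressly define, means day 7 or discharge. The second affects only the length of the recorded duration, not the failure of the rules.

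The correction should be made, but the stakes are modest. The primary outcome definition and the sample size are unaffected. What is at risk is the interpretability of one secondary outcome and its use in planning the later trial.

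**What to change.** In Section 3.3, change the leukocytosis threshold to a white blood cell count greater than 10,000 per microliter, and print that unit on the case report form and beside the REDCap field. A range check on the REDCap entry would be a sensible addition; the document does not describe one.

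In the same edit, state which of the two consecutive negative counts ends the duration.

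The platelet limits deserve a look at the same time. Exclusion criterion 2 in Section 4.3 uses 50 per microliter, while Section 4.4 describes the baseline exclusion as 50,000 per microliter. The two passages contradict each other and must be reconciled.

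The unit correction is one word and the clarification one sentence. Neither adds visits, samples or patients; the only cost is the administrative handling of the amendment.
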